3.2 Study Design Overview

The study is designed as a prospective, non-randomized, multicenter pivotal study to evaluate the safety and effectiveness of the CellFX System in patients with non-genital warts, excluding the face. Macrophotography of all treated warts will be captured along with Investigator assessments using a wart measurement scale and tissue response. One of the warts for each subject will be untreated and will serve as the subject's internal control. Please note the Investigator has the option at baseline and at each follow-up visit for curettage of the targeted site prior to NPS treatment. Additionally, at the 30-day, 60-day and 90-day visits the Investigator has the option to retreat any previously treated lesion.

3.3 Site Selection and Number of Subjects

Up to 6 clinical sites will participate in this study. Sites will be selected based on the appropriate patient population, physician experience in the treatment of warts, and adequate resources to support this pivotal study.

Approximately 60 subjects at 6 sites will be enrolled. A site may enroll up to 18 subjects in this study.

3.4. Clinical Study Duration

It is anticipated that the enrollment of subjects in this pivotal study will take approximately 4-months. All subjects included in this clinical investigation will return for follow-up visits at 7, 30, 60, 90 and 120-days post-initial NPS treatment. All lesions will have the possibility of being retreated up to 3 times, with a maximum of 4 total NPS treatments over the course of the study. Total study duration is approximately 8 months.

3.5 Enrollment Definition

For the purposes of enrollment, only those patients who meet all eligibility criteria, sign an IRB

approved consent form and begin treatment with the CellFX device will be considered enrolled in the study. Patients who consent to participate but withdraw prior to the first treatment with CellFX device will be considered a screen failure and this should be documented on the site screening log.

3.6 Study Evaluations

3.6.1 Primary Assessment:

The primary effectiveness evaluation of this study is reduction in wart size and/or clearance using the following wart measurement scale for each treated wart. (**See Table 1**)

Table 1: : Wart Measurement Scale

Rate of Reduction (%)	Scale Value
0-9	4
10-29	3
30-49	2
50-90	1
Clear	0

3.6.2 Secondary Assessment:

The secondary effectiveness evaluation of this study is subject satisfaction.

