4.3 Study Visits

4.3.1 Screening/Baseline Procedures including NPS Treatment – Visit 1 (Day 0)

The following evaluations and procedures are required at the time of subject screening/baseline

- Signed Informed Consent
- Dermatologic Medical History/Demographics
- Wart classification and anatomic location for all study lesions
- Inclusion and Exclusion criteria

Activities on 1st Study Visit Day - NPS Treatment Day

The following assessments and procedures will be performed

- Using a randomization method, the selected wart(s) will be designated to be treated and one will be designated as an untreated control.
- Each selected lesion will be numerically labeled, and photographic images will be taken before the local anesthetic/numbing.
- Local anesthetic/numbing will be administered to all study lesions.
- NPS treatment #1 will be delivered to all lesions.

- Subject will rate the level of pain from a specified pain score.
- Photographic images of all lesions will be taken immediately post-NPS treatment.
- A light bandage and any PI recommended dressing may be applied.
- Adverse event assessment will be performed.

4.3.2 7-Day Follow-up – Visit 2

The following assessments and procedures will be performed

- Photographic images of all study lesions will be taken.
- Each lesion will be clinically assessed, and the appearance will be rated according to specified criteria.
- Adverse event assessment will be performed.

4.3.3 30-Day Follow-Up / Possible NPS Re-Treatment - Visit 3

The following assessments and procedures will be performed

- Photographic images of all study lesions will be taken.
- Wart reduction assessment, including measurement will be performed.
- All lesions will be clinically assessed, and the appearance will be rated according specific criteria.
- All lesions that are rated other than “Clear” are eligible to receive a retreatment with NPS of those lesions.
- In case of an NPS retreatment:
 - Images of each of the selected lesions will be taken before local anesthetic/numbing and after the NPS treatment.
 - Local anesthesia/numbing will be applied to the identified lesions.
 - NPS treatment will be delivered.
 - Subject will rate the level of pain from a specified pain score.
 - A light bandage and any PI recommended dressing may be applied.
- Adverse event assessment will be performed.

4.3.4 60-Day Follow-Up / Possible NPS Re-Treatment - Visit 4

The following assessments and procedures will be performed

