- Photographic images of all study lesions will be taken.
- Wart reduction assessment, including measurement will be performed.
- All lesions will be clinically assessed, and the appearance will be rated according specific criteria.
- All lesions that are rated other than “Clear” are eligible to receive an NPS retreatment of those lesions.
- In case of an NPS retreatment:

- Images of each of the selected lesions will be taken before local anesthesia/numbing and after the NPS treatment.
- Local anesthesia/numbing will be applied to the identified lesions.
- NPS treatment will be delivered.
- Subject will rate the level of pain from a specified pain score.
- A light bandage and any PI recommended dressing may be applied.

- Adverse event assessment will be performed.

4.3.5 90-Day Follow-Up / Possible NPS Re-Treatment- Visit 5

The following assessments and procedures will be performed

- Photographic images of all study lesions will be taken.
- Wart reduction assessment, including measurement will be performed.
- All lesions will be clinically assessed, and the appearance will be rated according specific criteria.
- All lesions that are rated other than “Clear” are eligible to receive an NPS retreatment of those lesions.

- In case of an NPS retreatment:
 - Images of each of the selected lesions will be taken before local anesthetic/numbing and after the NPS treatment.
 - Local anesthesia/numbing will be applied to the identified lesions.
 - NPS treatment will be delivered.
 - Subject will rate the level of pain from a specified pain score.
 - A light bandage and any PI recommended dressing may be applied.

- Adverse event assessment will be performed.

4.3.6 120-Day Follow-Up – Visit 6 (Final Study Visit)

The following assessments and procedures will be performed

- Photographic images of all study lesions will be taken.
- Wart reduction assessment, including measurement will be performed.
- All lesions will be clinically assessed, and the appearance will be rated according specific criteria.
- Adverse event assessment will be performed.
- Subject satisfaction will be evaluated for the appearance of the treated lesions.

Table 2 lists assessments and procedures required at each study visit.

Table 2 : Schedule of Events and Evaluations

Study Visit Interval	#1 0-days Enrollment NPS TX #1	#2 7-days Post-NPS TX #1	#3 30-days Post-NPS TX #1	#4 60-days Post-NPS TX #1	#5 90-days Post-NPS TX #1	#6 120-days Post-NPS TX#1 (Final Visit)

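### The primary effectiveness evaluation covers treated warts only and leaves out the untreated control wart that the design gives each subject; the all-lesions treatment wording also conflicts with that control

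*Protocol*

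**What the plan says.** **Design.** Protocol section 3.2 states: "One of the warts for each subject will be untreated". That wart is to act as the subject's internal control. Section 4.3.1 chooses it by a randomization method: among the selected warts, "one will be designated as an untreated control".

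**Primary evaluation.** Section 3.6.1: "The primary effectiveness evaluation of this study is reduction in wart size and/or clearance using the following wart measurement scale for each treated wart". Table 1 then gives a five-level scale from 4 (0-9% reduction) to 0 (clear).

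**Other evaluations.** The only secondary evaluation is subject satisfaction (3.6.2), which section 4.3.6 ties to the treated lesions. In section 3.1 the clearance objective concerns the treated area, and the wart-reduction objective counts warts without naming a comparison.

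**Data collected.** Section 3.2 says "Macrophotography of all treated warts will be captured". The visit lists in section 4.3 go further: they photograph all study lesions and clinically assess each or all lesions from day 7 to day 120, with a wart reduction assessment from day 30.

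**Who is treated.** Section 4.3.1: "NPS treatment #1 will be delivered to all lesions". On later treatment, section 3.2 says "the Investigator has the option to retreat any previously treated lesion". Section 3.4 opens retreatment to all lesions. At day 30 (4.3.3), lesions not rated Clear "are eligible to receive a retreatment with NPS of those lesions"; at days 60 and 90 (4.3.4, 4.3.5) they "are eligible to receive an NPS retreatment of those lesions". None of these later passages excepts the control.

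**The concern.** The design pays for a concurrent within-subject control, chosen by chance and followed to day 120, but the primary evaluation is defined so that it plays no part. What is left is a reduction or clearance rate in treated warts. Section 1.1 describes warts as usually self-limited, so some treated warts would be expected to shrink or clear within 120 days without the device. A treated-only rate credits all of that to the device. In a study that calls itself pivotal, this decides what the main result can mean.

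The second part concerns the control itself. The comparison is informative only if it is clear whether the control wart receives the device, and the passages on treatment do not agree on this.

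**Working it through.** The protocol gives no target rate, alpha, power or success criterion behind its approximately 60 subjects, so it has no figure to reproduce. The check is a comparison of passages, followed by a sizing from the protocol's own feasibility data.

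**1. Lesion scope, side by side**

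| Place | Lesions covered |
|---|---|
| 3.2, 4.3.1 (design) | treated warts plus one untreated control |
| 4.3.2 to 4.3.6 (assessment) | all lesions |
| 3.6.1 (primary) | each treated wart |
| 3.6.2 with 4.3.6 (satisfaction) | treated lesions |
| 3.1 (clearance objective) | treated area |
| 3.1 (reduction objective) | total number of warts, no comparison named |

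Control data are collected, but no stated evaluation sets them against the treated warts.

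**2. Clearance without treatment.** Inputs from the feasibility study in section 1.4: 19 control warts, two with complete reduction; 34 warts identified for treatment, 50% with complete reduction.

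- Control clearance: 2/19 = 10.5%. Exact (Clopper-Pearson) 95% CI: 1.3% to 33.1%.
- Difference: 50.0 − 10.5 = 39.5 points (39.47 before rounding).
- Interval for the difference (Newcombe, independent proportions), assuming 50% means 17/34. Wilson limits are 34.1% to 65.9% for 17/34 and 2.9% to 31.4% for 2/19.
 - Lower: 39.5 − √[(50.0 − 34.1)² + (31.4 − 10.5)²] = 39.5 − 26.3 ≈ 13.
 - Upper: 39.5 + √[(65.9 − 50.0)² + (10.5 − 2.9)²] = 39.5 + 17.7 ≈ 57.

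This is rough. It ignores several warts per subject and the pairing with the control. The counts do not fully reconcile either: 34 + 19 = 53 against 58 warts stated, and the response categories sum to 50 + 21 + 26 = 97%. The feasibility control is also called a sham, whereas here it is untreated.

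**3. Would about 60 subjects support the comparison?** Illustration only: exact McNemar test on clearance, 60 pairs, one treated wart each, two-sided 0.05, independence within pair, treated clearance 50%.

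| Assumed control clearance | Power |
|---|---|
| 10.5% | 99.7% |
| 20% | 90.7% |
| 25% | 74.9% |
| 33.1% | 38% |

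Power stays at or above 80% up to a control clearance of 23.6%. If treated clearance were 60% or 70%, the limit would be 32.7% or 42.9%. The 50% comes from one or two treatments, while this protocol allows up to four.

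**4. Treatment of the control.** In section 4.3.1 the first item of the treatment-day list designates an untreated control, and a later item of the same list delivers treatment #1 to all lesions. Both cannot hold literally. For retreatment, section 3.2 limits it to lesions already treated, while 3.4 and 4.3.3 to 4.3.5 speak of all lesions, or all not rated Clear.

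**The case against.** **The analysis may belong to the SAP.** Section 3.6.1 names a scale and the lesions it scores; it gives no hypothesis or test. Section 3.2 gives the untreated wart a comparative role by calling it a control, and how the two are contrasted is commonly left to the SAP, which is not at hand. This stands in part: a missing test or model is no finding. But the protocol itself fixes which lesions the primary covers, and that scope omits the control. An SAP could add a comparison, but under 3.6.1 the treated-only result would remain the primary one. A reader might go further and infer that the control is not followed, or that no comparison will ever be made. The documents do not support that, since section 4.3 assesses all lesions.

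**The retreatment wording can be read consistently.** A wart never treated cannot be retreated, and section 3.2 states that limit. This largely stands. A reader might infer that the plan sends most control warts to treatment at days 30 to 90; the documents do not show this and give no basis for estimating how many controls would be treated. What remains is the literal clash over treatment #1 in section 4.3.1, and retreatment wording that does not except the control.

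**An immune effect may reach the control.** Section 1.4 reports an immune effect in mice, and the feasibility report suggests one for the two cleared controls. A sponsor might therefore prefer the control as supportive evidence. The point is fair, and two events cannot distinguish spontaneous clearance from an immune effect. But it does not make an uncontrolled rate easier to interpret.

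**Conclusion.** The concern holds on the text. The primary evaluation is limited to treated warts although a control designated by a randomization method is present and already assessed, and no stated evaluation compares the two. Followed as written, the primary result is an uncontrolled rate.

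The best guide to size in the document is the feasibility study: a treated-only figure of 50% becomes a controlled difference of about 39 points, plausibly anywhere from 13 to 57. That rests on reading 50% as 17 of 34, on treating warts as independent, and on preliminary counts that do not add up, so it shows order of magnitude only. The power figures are illustrative, and the conclusion does not depend on them.

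On procedures, the supported claim is narrow. The delivery of treatment #1 in section 4.3.1 contradicts the untreated control in section 3.2 and in its own list, and the later retreatment passages leave the control's status unstated. This is worth fixing before the study relies on the control.

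**What to change.** 1. In section 3.6.1, apply Table 1 to the control wart as well as to the treated warts. Define the primary as the within-subject comparison of treated with control warts at the 120-day visit, for example on clearance, with a method that allows for several treated warts per subject.
2. In section 3.2, align the photography sentence with section 4.3, which already covers all study lesions.
3. Reconcile sections 3.2, 3.4, 4.3.1 and 4.3.3 to 4.3.5 on whether the control wart receives first treatment or retreatment. This review does not say which rule is right, but the comparison depends on the answer.

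**Cost.** Protocol wording and analysis work; no new visits or procedures, because the assessments are already scheduled. The headline becomes a smaller, controlled difference, and it understates the device effect if treating one wart has an immune effect on the control. Whether about 60 subjects suffice depends on both clearance rates, so the sponsor should state the rates it assumes.

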4.0 STUDY PROCEDURES

4.1 Subject Selection

4.1.1 Inclusion Criteria:

Subjects are required to meet **ALL** inclusion criteria in order to be enrolled in the study.

1. Subjects must be at least 21 and not older than 80 years of age.
2. Subjects must be able to read and speak English or Spanish.
3. Subjects must sign a written informed consent to participate in the study, prior to any study related procedures.
4. Subject must have a minimum of two cutaneous non-genital warts, each not exceeding 10 x 10mm.
5. Subject is willing to undergo all study-mandated procedures.
6. Subject agrees to refrain from using all other wart removal products or treatments (topical medication including over-the-counter medications) during the study period.

4.1.2 Exclusion Criteria:

Subjects who meet **ANY** of the following exclusion criteria will not be enrolled in this study.

1. Subject has an implantable electronic medical device. (pacemaker, implantable cardioverter defibrillator, etc.)
2. Subject has cochlear implants.
3. Subject has an active systemic infection or history of an infection in the designated treatment area within 90 days of enrollment.
4. Subject has a history of and/or current tinnitus.
5. Subject is known to be immune-compromised.
6. Subject is taking a blood thinning medication (Antiplatelet, Anticoagulation, Factor Xa Inhibitor, etc.)
7. Subject has Type 1 Diabetes and is insulin dependent.
8. Subject has a known allergy to Lidocaine or Lidocaine-like products.
9. Subject is a member of a vulnerable population including individuals employed by the Sponsor, clinic site, or entity associated with the conduct of the study.
10. Subject has a comorbidity or condition which may reduce compliance with this protocol, including follow-up visits.
11. Subject is participating in another research study involving an investigational agent (pharmaceutical, biologic, or medical device).

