1.2 Non-Surgical Approach

Chemical Destruction:

Salicylic Acid

The use of salicylic acid is one of the two most commonly used treatments for warts. Dermatologists prescribe chemical destruction treatments where patients apply an over-the-counter preparation, usually less than 17% salicylic acid or prescription salicylic acid containing up to 70% salicylic acid at home every day. Treatment response rates of 40-84% with an average of 61% have been reported as an effective therapy for non-genital cutaneous warts.¹ Minor skin irritation was reported occasionally in some of the other trials, but generally there were no major harmful effects of topical salicylic acid.² A systematic review of local treatments of cutaneous warts by Mitsuishi et al., found evidence that topical treatments with salicylic acid have a therapeutic effect, with a cure rate of 75 percent compared with 34-48 percent in placebo controls.^{1,3} Other agents used for chemical destruction are monochloracetic acid, dichloracetic acid, trichloroacetic acid, silver nitrate, glycolic acid and 80% phenol in solution. Complications associated with using chemicals include pain, hyperpigmentation, hypopigmentation, burning sensation and erythema.⁴

Cantharidin

Cantharidin is used as an agent in the clinic by "painting" the wart causing oxidative stress by inhibiting phosphatases 1 and 2A that damages both DNA single- and double-strand breaks and triggers p53 dependent apoptosis.⁴ Cantharidin causes a blister to form under the wart. In a week or so, the patient returns to the office and the dermatologist clips away the dead wart.

Immune Modulators

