This treatment uses the patient's own immune system to fight the warts. Forms of immune modulators include imiquimod, intralesional immune modulators using Candida antigen or anti-cancer such as Bleomycin; contact immunotherapy, cimetidine, zinc, and retinoids. Because wart proliferation is controlled by the immune system, various methods have been used to stimulate the immunologic response to HPV. This treatment is used when the warts remain despite using other treatments and the ability to treat many lesions simultaneously. One type of immunotherapy involves applying a chemical diphenylcyclopropenone (DPCP). Among these are topically applied inorganic molecules capable of eliciting contact hypersensitivity, such as imiquimod and intralesional interferons⁵ to the warts. A mild allergic reaction occurs around the treated warts which stimulates the body's innate response to fight the virus.

Physical Destruction:

Cryotherapy

For common warts in adults and older children, cryotherapy is a standard treatment and can be done in the physician's office. Cryotherapy involves freezing a wart using a very cold substance (usually liquid nitrogen). The liquid nitrogen application usually takes less than a minute and most warts require 1 to 4 treatments, with 1 to 3 weeks between each treatment. Pain from cryotherapy can last up to 3 days. Healing is generally quick (7 to 14 days) with little or no scarring⁶. It can cause dark spots in people who have dark skin. With cryotherapy, it is common for repeat treatments.

Laser

Laser treatment is an option, mainly for warts that have not responded to other therapies. Before laser treatment, the dermatologist may numb the wart with an anesthetic injection.

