Nineteen (19) treated adult subjects were required to have 2-5 non-genital, off-face cutaneous warts in this multi-center feasibility study. Up to four warts were designated to be treated, while one wart was designated as the sham control. Subjects received an initial NPS-treatment and returned for 3 to 5 follow-up evaluations at 7 days, 30 days, 60 days, 90 days and 120 days after the initial treatment. Each wart was evaluated for size reduction and the condition of the skin. If the reduction in wart size met study criteria, the wart was eligible for an additional treatment and at the discretion of the investigator.

Six (6) of the 19 subjects were male and 13 were female. Ages ranged from 23 to 71, with an average age of 48. Subjects had Fitzpatrick skin types ranging from I to III. A total of 58 warts have been included in the study at the time of this report. 34 warts were identified for treatment and 19 warts as controls. 70% of the study warts had been previously treated with another modality and were not successful at eliminating the wart. 69% of treated warts were located on the hand/fingers and the remaining 31% of treated were located on the feet. Twenty-five (25%) of treated warts received a single treatment, and 75% received two treatments. Of the treated warts, 50% showed 100% reduction in size, 21% showed a 50-90% reduction in size, and 26% showed less than a 50% reduction in size at the last reported visit. Twenty-nine (29%) of the treated warts showed 100% reduction after a single treatment. There were two instances where the control wart showed 100% reduction in size, suggesting that there may be an immune response. Preliminary data analysis indicates that complete coverage of the wart within the treatment zone is required. There is also a trend toward the use of higher settings within the allotted range for better outcomes. There were no instances of hypopigmentation noted, and 3 cases of mild hyperpigmentation at 60 days.

The high rate of wart size reduction suggests the utility of the unique NPS cellular mechanism for the treatment of non-genital, cutaneous warts. Based on these initial results, a larger pivotal study is warranted and will be conducted in the future to further evaluate the use of NPS technology for the treatment of warts.

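### Eligibility sets no minimum time since the last treatment of a study wart, so carry-over clearance could be counted as NPS response in the treated-wart primary evaluation

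*Protocol*

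**What the plan says.** Protocol Section 4.1.1, criterion 6, is the only restriction on other wart therapy: "Subject agrees to refrain from using all other wart removal products or treatments (topical medication including over-the-counter medications) during the study period". It takes effect once the subject is in the study.

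The exclusions in Section 4.1.2 contain one explicit look-back in days, and it concerns infection: "Subject has an active systemic infection or history of an infection in the designated treatment area within 90 days of enrollment". Exclusion 11 concerns other research, but in the present tense: "Subject is participating in another research study involving an investigational agent (pharmaceutical, biologic, or medical device". It reaches concurrent participation only, so a wart treated in a completed NPS study is not barred.

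Section 4.3.1 places consent, history, eligibility, wart selection and NPS treatment #1 at Visit 1, Day 0. A dermatologic history is taken, but the protocol does not tie prior treatment to eligibility or to the choice of study warts.

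Section 3.6.1 defines the outcome: "The primary effectiveness evaluation of this study is reduction in wart size and/or clearance using the following wart measurement scale for each treated wart". Section 3.2 adds a control: "One of the warts for each subject will be untreated and will serve as the subject's internal control". Section 4.3.1 says that wart is designated by a randomization method, which it does not describe. Section 3.6.1 names no comparison with it.

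**The concern.** A patient part-way through another course of wart therapy meets every written criterion if that therapy stops at enrolment. The protocol's background shows that such courses can straddle Day 0. Section 1.2 says of cryotherapy that "most warts require 1 to 4 treatments, with 1 to 3 weeks between each treatment", and it describes salicylic acid as a daily home treatment. Section 9.2 says subjects come directly from the investigators' own candidates for wart removal.

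If a wart was treated shortly before Day 0 and then clears because of that treatment, the primary evaluation has no means of telling this from an NPS effect. The treated-wart response rate would be biased upward, with nothing in the data to show it. A second, smaller issue is appearance. A site still healing from an earlier procedure could affect the baseline from which reduction is judged, and the Day 7 skin rating.

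A later analysis plan can choose the contrast and the sensitivity analyses. It cannot create an eligibility rule, and it cannot recover a treatment date that was never recorded.

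**Working it through.** **Text check.** The 6 inclusion and 11 exclusion criteria, the Visit 1 steps and the schedule in Table 2 were read for any limit on treatment before Day 0. There is none. The protocol states no figure on this point, so there is nothing to reproduce. What follows is illustration under stated assumptions.

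**Inputs**
- p, true NPS clearance: 0.50, the share of treated warts with 100% reduction in the feasibility study (Section 1.4).
- p0, clearance of untreated warts: 2/19 = 0.105, from two cleared controls among 19 control warts in the same study.
- f, share of study warts recently treated by other means: 0.10 to 0.30, assumed. The documents give no figure.
- c, chance that the earlier treatment clears the wart after Day 0: 0.20 to 0.41. The lower value is assumed. The upper is the largest salicylic acid difference over placebo in Section 1.2, 75% − 34% = 41 points.
- Carry-over is taken as independent of NPS.

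**Treated-wart rate.** Observed rate = p + f·c·(1 − p), so inflation = f·c·(1 − p).

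**Treated-versus-control contrast.** If the control wart is chosen at random, f and c are the same in expectation for both kinds of wart. The observed control rate is p0 + f·c·(1 − p0). Subtracting gives (p − p0)(1 − f·c). The true difference is 0.500 − 0.105 = 39.5 points.

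| f | c | f·c | Treated-wart rate | Inflation (points) | Contrast (points) | Loss (points) |
|---|---|---|---|---|---|---|
| 0.10 | 0.20 | 0.020 | 51.00% | +1.00 | 38.7 | 0.8 |
| 0.10 | 0.41 | 0.041 | 52.05% | +2.05 | 37.9 | 1.6 |
| 0.30 | 0.20 | 0.060 | 53.00% | +3.00 | 37.1 | 2.4 |
| 0.30 | 0.41 | 0.123 | 56.15% | +6.15 | 34.6 | 4.9 |

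So the uncontrolled rate rises by about 1 to 6 points, and a controlled contrast shrinks by about 1 to 5.

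**Skin ratings.** Section 1.2 gives cryotherapy healing as 7 to 14 days. Table 2 puts Visit 2 at days 5-9 and Visit 3 at days 27-37. A site frozen up to 9 days before Day 0 could still be within 14 days of treatment at the earliest Visit 2 (9 + 5 = 14). At Visit 3, any site frozen before Day 0 is at least 27 days old. Baseline and Day 7 can be affected; on the protocol's own healing time, Day 30 is not.

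**The case against.** The strongest reply is that nothing shows the problem will arise often. The feasibility report says that "70% of the study warts had been previously treated with another modality and were not successful at eliminating the wart", and a reader might infer that recently treated warts will be common. The sentence does not support that: it counts warts ever treated and gives no timing. Being a candidate for removal (Section 9.2) does not mean being in mid-course. Entering f = 0.70 would give 0.70 × 0.41 × 0.50 = 14.4 points of inflation, but that treats every past treatment as recent, which the documents do not say. This objection stands in full against any claim about frequency.

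The same sentence says those treatments failed. A wart still present at Day 0 has been selected for non-response, so its carry-over chance may be low. Nor can the background statement that "Treatment response rates of 40-84% with an average of 61% have been reported" serve as a carry-over probability: it describes response to treatment in use and is not net of placebo. For this reason c is capped at 0.41, which is still generous for residual effect.

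The randomized control wart also matters. A reader might infer that the trial's controlled comparison would favour the device. With random designation, prior treatment balances in expectation and carry-over pulls the contrast toward zero. That stands too, but it protects only an analysis that uses the control, and Section 3.6.1 as written scores treated warts alone.

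Finally, entry of warts previously treated with NPS is possible under the criteria, but nothing indicates that any of the 19 feasibility subjects would re-enrol.

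None of this supplies the missing rule.

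**Conclusion.** The gap is real and can be checked in the text: the protocol bars other wart treatment during the study but sets no interval before it and does not bar warts already treated with NPS. The consequence is conditional. Where a wart was recently treated, carry-over clearance could be credited to NPS in the treated-wart evaluation, and baseline and Day 7 appearance could be disturbed.

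Under the assumptions shown (10-30% recently treated, 20-41% carry-over, 50% true clearance, independence), the treated-wart rate is inflated by about 1 to 6 points. The actual size is unknown, because the documents give neither the frequency nor the timing of prior treatment. The direction for that rate is upward; a treated-versus-control contrast would be diluted. The documents do not support saying that such clearance will certainly be counted, that recent treatment will be common, or that Day 30 skin ratings are affected. The point merits correction because this is a pivotal study whose primary measure is treated-wart response, and because the remedy must be in the protocol.

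**What to change.** Add a wart-level eligibility rule in Section 4.1: no wart may be selected as a treated or control study wart if it received any wart treatment (topical, procedural, intralesional or immunotherapy) within a fixed look-back before Day 0, or if it was ever treated with NPS. The sponsor should set the length and justify it on clinical grounds; the documents give no basis for a particular number of days.

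Record the last modality and its date for each study wart at Visit 1, within the dermatologic history already taken. This would allow a sensitivity analysis that excludes recently treated warts, and would show how many there were.

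The cost is one added criterion and two data fields per wart. Some candidates would wait or contribute other warts, so the planned enrolment of about 4 months may run slightly longer.
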